11.3. Data Analysis Considerations

11.3.1. Analysis Populations

The safety population will include all subjects who receive at least 1 dose or partial dose of study drug. All safety and pharmacodynamic analyses will be performed using the safety population.

The Stage 1 PK population will include all subjects who have a complete set of sparse PK samples from the single day of collection at steady-state between Day 15 and Day 30 of Stage 1.

The final PK population will include all subjects with at least one quantifiable concentration and a known weight and eGFR. All final PK analyses will be performed using the final PK population.

The intent-to-treat population will include all enrolled subjects. All efficacy analyses will be performed using intent-to-treat population.

11.3.2. Statistical Methods

Data will be summarized using descriptive statistics. Continuous variables will be summarized by number of subjects, mean, standard deviation, median, minimum, and maximum values. Discrete variables will be summarized by counts and percentages.

In general, data will be summarized by sex and combined across all subjects.

A month will be defined as 30 days.

No missing data imputation method is planned to handle missing data. Data will be summarized as observed. All data will be listed.

11.3.2.1. Interim Analysis

The interim PK endpoint is a graphical presentation of plasma-concentration time data (observed versus predicted).

Interim analysis of the plasma concentration-time data collected during Stage 1 will be conducted when these results are available. There will be 2 interim PK analyses. One analysis will be performed using the entire Stage 1 PK population of adolescents aged 12 to < 18 years. A second analysis will include a subpopulation of at least 7 to 10 subjects age 12 to < 16 years.

11.3.2.2. Safety Analyses

Adverse events will be coded using the Medical Dictionary for Regulatory Activities (MedDRA) and summarized by system organ class and preferred term. Summaries will be provided for TEAEs, TEAEs by severity, and TEAEs by relationship to study drug as well as deaths, SAEs, and TEAEs leading to discontinuation of study treatment. Listings will also be provided for SAEs and TEAEs leading to discontinuation of study treatment.

Actual values and changes from baseline for clinical laboratory test results, vital signs, body weight and height, ECG parameters, echocardiogram parameters (other than LVMi) and Tanner stages will be summarized using descriptive statistics. Shift tables will also be provided for clinical laboratory tests and ECG results. Physical examination findings will be summarized by body system.

Concomitant medications will be coded using the World Health Organization (WHO) Drug Dictionary and will be summarized by Anatomical-Therapeutic-Chemical classification.

11.3.2.3. Pharmacokinetic Analyses

For the population PK analysis, predicted median (2.5^{th} and 97.5^{th} percentile) concentration-time data based on a previously established population PK model will be visually compared with observed concentration-time data for all patients and for the subgroup aged 12 to < 16 years at the end of Stage 1.

The PK analyses for the current study will be performed according to the following steps:

- Step 1: After combining previous concentration-time data from adults with pediatric data from the current study, the population PK model established previously (Migalastat Amended Population Pharmacokinetic Analysis of Migalastat, Amendment 02; Migalastat Abbreviated Report of the Simulations of Migalastat in Pediatric Patients with Fabry Disease, 20 October 2016) will be updated. Most importantly, the allometric scaling functions for CL/F and volume parameters (ie, V2/F, V3/F) will be re-evaluated and corrected, if necessary. Other covariates that are predictive of drug disposition (eg, age, weight, body surface area) may be evaluated.
- Step 2: Using the updated population PK model, clinical trial simulations will be conducted assuming administration of migalastat to steady-state concentration for each pediatric subject and for adults (with equivalent renal function) receiving migalastat HCl 150 mg every other day. The simulations will use population PK parameter uncertainty from a nonparametric bootstrap, inter-individual variability, and residual variability. At least 1000 clinical trials will be simulated assuming at least 24 subjects per age group.
- Step 3: Pharmacokinetic endpoints (ie, C_{max}, C_{min}, and AUC_{0-τ}) for migalastat will be calculated from simulated concentration-time data in pediatric groups and in adults. The AUC_{0-τ} and C_{max} in 12 to < 18 year olds will be compared to the values in adults with equivalent renal function using an analysis of variance (ANOVA). The 90% confidence intervals (CIs) for the ratio of the geometric least squares means of C_{max} and AUC_{0-τ} will be constructed for comparison of the pediatric group with adult group. These 90% CIs will be obtained by exponentiation of the 90% CIs for the difference between the least squares means based on an In-transformed scale.
- Step 4: Exposures in the pediatric group and adults will be considered equivalent when 90% CIs of the ratio of the geometric least squares means of $AUC_{0-\tau}$ are within the range of 0.8 to 1.25 (ie, 80% to 125%). Intervals obtained from Step 3 will be evaluated according to these a priori criteria. The ratios and CIs will also be determined for C_{max} .
- Step 5: If the bioequivalence criteria cannot be met in Step 4 using the dosing regimen listed in Section 7.2.1, adjusted dosing regimens will be proposed to achieve bioequivalence considering dose proportionality, if necessary, and used for future pediatric clinical trial simulations.
- Step 6: The proposed dose for pediatric subjects (12 to < 18 years and 12 to < 16 years) will then be considered the dosage regimen producing an AUC_{0- τ} meeting the 80% to 125% rule and a C_{max} that either meets this rule or, if not possible, is as close as possible balancing the available dosage strengths with safety.

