11.1.2. Pharmacokinetic Endpoints

Pharmacokinetic endpoints are as follows:

- population PK model that describes the relationship between weight and age and migalastat pharmacokinetics in pediatric subjects (with primary PK parameter outputs listed in the following text)
- PK parameters based on simulated plasma-concentration data for migalastat after multiple-dose administration at steady-state concentration
 - C_{max}: maximum observed plasma concentration
 - C_{min}: minimum observed plasma concentration
 - t_{max}: time to reach C_{max}
 - AUC₀₋₇: area under the plasma concentration-time curve from time 0 over the dosing interval (ie, 48 hours)
 - t_{1/2}: terminal elimination half-life
 - CL_{ss}/F: apparent oral clearance at steady-state concentration
 - V_{ss}/F: apparent oral volume of distribution at steady-state concentration

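### Protocol Steps 2–3, read literally, take Cmax, Cmin and tmax from simulated concentrations that carry residual error, so their absolute values depend on an unstated error size and time grid

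*Protocol*

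**What the plan says.** Protocol Section 11.3.2.3 sets out the pharmacokinetic analysis in six steps.

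- **Step 2** lists what enters the simulations: "The simulations will use population PK parameter uncertainty from a nonparametric bootstrap, inter-individual variability, and residual variability". It adds: "At least 1000 clinical trials will be simulated assuming at least 24 subjects per age group".
- **Step 3** says that Cmax, Cmin and AUC0-τ "will be calculated from simulated concentration-time data in pediatric groups and in adults".
- **Step 4** declares equivalence on AUC0-τ alone, with the 90% confidence interval inside 0.80 to 1.25. For Cmax it says only: "The ratios and CIs will also be determined for" that parameter.
- **Step 6** looks for a regimen whose AUC0-τ meets the 80–125% rule, with a Cmax "that either meets this rule or, if not possible, is as close as possible balancing the available dosage strengths with safety".

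Protocol Section 11.1.2 describes the endpoints consistently with Step 3: "PK parameters based on simulated plasma-concentration data for migalastat after multiple-dose administration at steady-state concentration". Cmax, Cmin, tmax and AUC0-τ are all listed there. Sections 11.3.2.4 and 11.3.2.5 plot simulated AUC0-τ and Cmax against the pharmacodynamic and efficacy endpoints.

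No section says that exposure metrics come from error-free individual predictions, and none gives the residual error size or the simulation time grid. SAP Section 9 defers the PK analysis to a separate PKAP.

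**The concern.** Residual variability is assay and model error. It belongs in a simulated *measurement*, not in a subject's exposure. If it is added at every simulated time point, the maximum of the curve is the largest of several noisy values around a fairly flat peak. On average that exceeds the true peak, and a finer grid gives more values to choose from. The minimum over noisy late points falls too low by the same mechanism, and the time of the maximum wanders. AUC is protected because it averages the errors.

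These parameters are listed endpoints that serve a Stage 1 primary objective (Protocol Section 6.1). Two analysts who follow the same text with different grids could report different absolute Cmax values from the same fitted model. In the exposure-response plots, the error also adds scatter to the Cmax axis that has nothing to do with exposure.

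**Working it through.** **No plan figure to reproduce.** The documents give no simulated Cmax, residual error size or grid. The check therefore shows direction and a range, not a value for this trial.

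**Inputs from the documents.** Protocol Table 2, 150 mg row: t½ 3.8 h, median tmax 3.0 h, Cmax 1700 ng/mL, AUC 10,654 ng·h/mL. Dosing interval 48 h (Section 11.1.2). Inter-individual variability 28.5% (Section 11.2).

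**Assumptions.** Independent log-normal residual error of 10%, 20% or 30% at each time point; grids of 2, 1, 0.5 and 0.25 h.

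**Formula.** With true curve C(t) and errors e_j, the literal reading gives Cmax* = max over j of C(t_j)·exp(e_j). The quantity checked is the geometric mean of Cmax* divided by that of the true peak.

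**Hand check of the mechanism.** For three equally high points with error SD 0.20, the expected maximum of three standard normals is 3/(2√π) = 0.846. The expected inflation is then exp(0.20 × 0.846) = 1.18, so a double-digit effect at 20% error is plausible.

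**Two curves.**
- *Curve A*: one compartment, ke = ln 2/3.8 = 0.182/h, ka = 0.551/h (tmax 3.0 h). Its peak is AUC × ke × exp(−ke × 3) = 10,654 × 0.1824 × 0.5786 ≈ 1124 ng/mL, well below 1700. It is too flat, so it overstates the inflation.
- *Curve B*: gamma absorption with biexponential decline, fitted to Table 2 (Cmax about 1693, tmax 2.7 h, AUC about 10,683), with between-subject variability.

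Inflation factor for geometric mean Cmax:

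| Grid | A: 10 / 20 / 30% error | B: 10 / 20 / 30% error | B, no residual error |
|---|---|---|---|
| 2 h | (see below) | 0.95 / 0.98 / 1.03 | 0.94 |
| 1 h | 1.05 / 1.15 / 1.25 | 1.02 / 1.08 / 1.18 | 0.98 |
| 0.5 h | 1.10 / 1.24 / 1.40 | 1.06 / 1.19 / 1.34 | 0.996 |
| 0.25 h | 1.14 / 1.33 / 1.54 | 1.11 / 1.28 / 1.49 | 0.999 |

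On a 2-h grid with 10% error, curve A is within about 1% of the truth and curve B is 5% low, because a coarse grid misses the peak.

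The error has mean 1 in curve A and median 1 in curve B. Putting the 20% column of B on a mean-1 footing divides it by exp(0.20²/2) = 1.020. That gives 1.078/1.020 = 1.06, 1.185/1.020 = 1.16 and 1.275/1.020 = 1.25. The direction and pattern are unchanged.

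**Other parameters, 20% error, curve A.** Cmin falls to between 0.89 (2-h grid) and 0.77 (0.1-h grid) of the truth. The 5th–95th percentile range of tmax runs from about 2 h to 5–6 h, although the true value is 3 h for everyone. Residual error alone gives log Cmax an SD of 0.11–0.14 on grids of 0.25–1 h. AUC changes by less than 0.2% with mean-1 error. With median-1 error it rises by the constant factor 1.02, which cancels in a ratio.

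**Pediatric/adult ratio with shared settings.** For curve B at 20% error on a 0.5-h grid, a true Cmax ratio of 1.247 becomes 1.237. Across all settings tried the shift is at most about 2%. The Cmax confidence interval barely widens. With 24 per group its half-width factor is exp(t × SD × √(2/24)) with t the 95th percentile on 46 df: 1.185 at a log SD of 0.35 and 1.196 at 0.37.

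**Ratio with different settings.** At 20% error with adults on a 1-h grid and adolescents on 0.25 h, a true ratio of 1.00 becomes 1.17. On a 0.5-h grid with error 0.20 in adults and 0.30 in adolescents it becomes 1.13.

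**The case against.** The strongest reply is that no planned decision turns on this. Step 4 tests AUC0-τ only. Step 6 holds Cmax to the 80–125% rule, which is a ratio and is nearly preserved. Protocol Section 5.6 explains that AUC was chosen as target because added risk is not expected with higher Cmax and changes in Cmin are unlikely to affect efficacy. All of this stands.

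A reader might infer that the reported Cmax would be set against the 1700 ng/mL of Table 2 and found wrong. The documents plan no such comparison. Step 3 compares simulated adolescents with simulated adults, and Table 2 holds single-dose maxima of measured samples, which carry assay error too. A reader might also infer that the ratio is distorted. That requires different grids or error models for the two groups. The text does not forbid this, but Steps 1 and 2 describe one updated model and one simulation exercise.

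The magnitudes rest on assumptions, and the one-compartment curve exaggerates them. That also stands, and it is why the lower, Table 2-calibrated figures are given beside it.

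Finally, Step 2 lists variance components and does not expressly say that error-laden values feed Step 3; the unseen PKAP may settle it. This is fair, but Step 3 names the simulated concentrations as its source without qualification. A PKAP that followed the protocol to the letter would carry the bias.

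**Conclusion.** The point holds in limited form. On the plain reading of Steps 2 and 3, absolute Cmax is too high on grids of 1 h or finer, Cmin is too low and tmax is scattered. At an assumed 20% error the Cmax excess is about 8–15% on a 1-h grid and 28–33% on a 0.25-h grid, with the lower figure of each pair from the curve calibrated to Table 2. These are illustrations, since neither the error nor the grid is stated. An upward bias is not certain: on a 2-h grid with 10% error it is nil or slightly negative.

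The affected outputs are the reported Cmax, Cmin and tmax endpoint values and the simulated Cmax in the exposure-response plots. A reader might conclude that the equivalence decision or the Step 6 dose proposal is compromised. The documents do not support that: AUC0-τ is essentially unaffected, and the Cmax ratio moves by at most about 2% when both groups share grid and error model.

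**What to change.** In Protocol Section 11.3.2.3, Steps 2–3, and in the PKAP:

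- Keep bootstrap parameter uncertainty and inter-individual variability in the simulations.
- Derive Cmax, Cmin, tmax and AUC0-τ from simulated individual predictions **without** residual error.
- State one time grid, 0.5 h or finer around the peak, and use it for both adolescents and adults. Without residual error, grids of 0.5 h or finer recover 0.996–1.000 of the true peak, so the grid then hardly matters.
- Use residual variability only for the observed-versus-predicted concentration plots.

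The cost is a few sentences and one simulation setting, with no extra data. If the PKAP already works this way, the protocol wording only needs to be brought into line with it.

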5.6. Justification for Proposed Dose and Regimen in Pediatric Subjects with Fabry Disease

Migalastat has not been studied in pediatric subjects under 16 years of age. Although adolescent subjects with Fabry disease 16 to < 18 years of age were included in Phase 3 studies, the number of adolescent subjects included in those studies was limited. Therefore, simulations have been performed (100 subjects per age group) to select doses that match exposure in pediatric patients to exposure observed in adults receiving migalastat HCl 150 mg QOD. Area under the plasma concentration-time curve over the dosing interval (AUC_{0-t}) at steady-state concentration was selected as the target parameter for dose selection in pediatric subjects because existing safety and tolerability data in adults suggest that increased risk is not expected with increases in C_{max} and that changes in minimum observed plasma concentration (C_{min}) are not likely to affect efficacy given there is likely an indirect relationship between plasma concentrations and efficacy. The aim is to achieve AUC values in pediatric subjects that are similar to those in adults with Fabry disease and with normal renal function who were receiving migalastat HCl 150 mg every other day.

The largest biological factor affecting migalastat plasma clearance (CL/F) is renal function. While many adult patients with Fabry disease have reduced renal function (15% and 42% of subjects in Study AT1001-011 with moderate or mild renal impairment, respectively, based on estimated glomerular filtration rate [eGFR]), pediatric patients with Fabry disease have relatively high values for eGFR (mean, 147 mL/min/1.73 m²) (Hopkin, Bissler et al. 2008).

Body weight also explains variability in the pharmacokinetics of migalastat in individuals < 70 kg, with effects on CL/F, volume of distribution in the central compartment (V2/F), volume of distribution in the peripheral compartment (V3/F), and distribution clearance (Q/F). These effects were incorporated into the dose rationale simulations for pediatric subjects by using the range of weights from the Centers for Disease Control and Prevention weight chart (data on file).

Lastly, there is a very small change in CL/F (15%) and V2/F (31%) in the presence of Fabry disease. This effect was accounted for in the simulations, even though these differences result in exposures that are similar to those reported for healthy subjects.

6. **OBJECTIVES AND PURPOSE**

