11.2. Sample Size Considerations

A sample size of at least 7 to 10 subjects per age/weight group is required for statistical comparison with adult exposure based on 2 methods described by Wang, Jadhav et al. 2012.

First, assuming the final CL/F estimates and inter-individual variability of 28.5% (Migalastat Abbreviated Report of the Simulations of Migalastat in Pediatric Patients with Fabry Disease, 16 October 2016), 7 subjects is adequate to achieve at least 80% power for a study design with rich PK sampling intended for non-compartmental analysis.

Second, according to the sample size calculation for a study with sparse/rich PK sampling intended for population PK analysis, $(e^{-t(0.975,df) \times SE_{LCL}}, e^{t(0.975,df) \times SE_{LCL}})$ should be within the pre-defined criteria of (0.6, 1.4), where SE_{LCL} is the standard error for log-transformed pediatric clearance that relates to weight, and t (0.975, df) is the 97.5% upper quantile values from t distribution corresponding to the sample size. Mathematically, SE_{LCL} was approximately equal to the relative standard error of untransformed clearance, 0.16. Therefore, a sample size of approximately 10 subjects is adequate to achieve the pre-defined boundary of (0.6, 1.4).

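### Exposure equivalence is judged by ANOVA confidence intervals on simulated subjects, so their width follows an unfixed simulated sample size and not the precision of the trial

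*Protocol*

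**What the plan says.** Protocol 11.3.2.3 sets out the analysis in steps.

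- **Step 2** simulates trials from the updated population model: "At least 1000 clinical trials will be simulated assuming at least 24 subjects per age group". On sources of variation: "The simulations will use population PK parameter uncertainty from a nonparametric bootstrap, inter-individual variability, and residual variability".
- **Step 3** derives exposure from the simulated profiles, compares 12 to < 18 year olds with adults of equivalent renal function by ANOVA on the log scale, and forms 90% confidence intervals for the geometric mean ratios of AUC and Cmax.
- **Step 4** gives the criterion: "Exposures in the pediatric group and adults will be considered equivalent when 90% CIs of the ratio of the geometric least squares means" of AUC over the dosing interval lie within 0.8 to 1.25. It adds: "Intervals obtained from Step 3 will be evaluated according to these a priori criteria".
- **Steps 5 and 6** follow from the result. A failure leads to adjusted regimens for later simulations. The 80-125% rule also governs the proposed dose, for 12 to < 18 and for 12 to < 16 years.

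The SAP adds no rule. Its sections 2.1, 5.3 and 9 leave PK to a separate PKAP. Section 13 refers Stage 1 interim PK to a separate interim SAP. Section 14 declares no change from the protocol.

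**The concern.** A confidence interval should show how well the data determine the quantity of interest. Here the ANOVA sees simulated subjects, and their number is the analyst's choice above a floor. Within one simulated trial, a bootstrap draw of the parameters shifts the group means and adds nothing to the residual mean square from which the interval is built. Parameter uncertainty therefore moves the ratio from one trial to the next but does not widen any single interval. If the trials were pooled, it would become extra scatter divided by a very large n. Either way, a larger simulated n narrows the interval with no further information from the adolescents enrolled.

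Step 4 is the only numeric pass/fail exposure rule in the protocol or SAP. It bears on the Stage 1 primary objective of validating extrapolation from adult exposure (Protocol 6.1), because the interim PK endpoint is graphical (Protocol 11.3.2.1). With n and the combining rule both open, the same fitted model could support different verdicts.

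**Working it through.** **Inputs**

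- Limits 0.80-1.25 and 90% intervals: Protocol 11.3.2.3, Steps 3-4.
- Simulated size: at least 24 per age group and at least 1000 trials (Step 2).
- Variability: "inter-individual variability of 28.5" per cent for clearance (Protocol 11.2), applied here to AUC (assumption). Log SD = sqrt(ln(1 + 0.285²)) = 0.2795.
- Alternative: single-dose AUC at 150 mg, 10,654 (SD 2612), Protocol Table 2. CV = 2612/10,654 = 0.245, so log SD = 0.2416.
- Range of assumption: log SD 0.20 to 0.40.
- Also assumed: equal groups with a common SD and no residual variability.

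**The plan's own figure.** The documents give no pass probability for Step 4. The stated figure that uses the 28.5% is 7 subjects for at least 80% power (Protocol 11.2, first method). Taking the target as a 95% interval within a factor of 1.4 (assumed to carry over from the second method), power = P(t(0.975, n−1) × s/√n < ln 1.4). At n = 7, s must be below 0.3365 × 2.646/2.447 = 0.364, which gives 88%. At n = 6 it gives 75%. With 0.285 used directly as the log SD, the figures are 87% and 72%. So 7 reproduces and the variability input is usable.

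**Reading 1: one interval centred on the estimated ratio.**
Half-width h = t(0.95, 2n−2) × SD × sqrt(2/n). An estimated ratio passes if it lies between 0.80 × exp(h) and 1.25 × exp(−h).

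At log SD 0.2795:

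| Simulated n per group | h | exp(h) | Passing ratios |
|---|---|---|---|
| 24 | 1.6787 × 0.2795 × 0.2887 = 0.135 | 1.145 | 0.92-1.09 |
| 100 | 0.065 | 1.067 | 0.85-1.17 |
| 1000 | 0.021 | 1.021 | 0.82-1.22 |
| 24,000 (1000 × 24 pooled) | 0.004 | 1.004 | 0.803-1.245 |

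Example: an estimated ratio of 1.15 has interval 1.00-1.32 at n = 24 (fails) and 1.08-1.23 at n = 100 (passes).

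Sensitivity, passing ratios at n = 24, 100 and 1000:

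| Log SD | n = 24 | n = 100 | n = 1000 |
|---|---|---|---|
| 0.20 | 0.88-1.13 | 0.84-1.19 | 0.81-1.23 |
| 0.2416 | 0.90-1.11 | 0.85-1.18 | 0.81-1.23 |
| 0.40 | 0.97-1.03 | 0.88-1.14 | 0.82-1.21 |

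At log SD 0.40 the ratio of 1.15 fails at both 24 and 100 and passes only at 1000.

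**Reading 2: share of simulated trials that pass.**
Monte Carlo, 400,000 replicates, log SD 0.2795. Between-trial SE of the log ratio is an assumption: 0, 0.16 (the planning value for clearance in Protocol 11.2, tied there to about 10 subjects), or 0.16 × sqrt(10/20) = 0.113 if it scales to 20 subjects.

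| True ratio | SE | n = 24 | n = 100 | n = 1000 |
|---|---|---|---|---|
| 1.00 | 0 | 72% | 100% | 100% |
| 1.00 | 0.113 | 47% | 81% | 92% |
| 1.00 | 0.16 | 38% | 66% | 79% |
| 1.10 | 0 | 45% | 94% | 100% |
| 1.10 | 0.113 | 39% | 68% | 82% |
| 1.10 | 0.16 | 33% | 59% | 72% |

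Parameter uncertainty weakens the dependence on n but does not remove it.

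**Reading 3: every one of 1000 intervals must pass** (independent trials, true ratio 1.00, no parameter uncertainty). The chance is about 2 × 10⁻¹⁴³ at n = 24 and 0.93 at n = 100.

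**The case against.** The strongest reply is that the PK detail belongs in the PKAP, which the SAP names and which may fix both n and the combining rule. That stands as a limit on scope: nothing here says these matters are unspecified everywhere. It does not rescue the criterion as written. A PKAP that merely fixed n and kept the ANOVA interval as the test would still report a width set by that n.

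A second reply is that Step 2 already includes bootstrap uncertainty. It does, and Reading 2 allows for it, but no single interval contains it.

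A third is that the reversal is conditional. This is right. At log SD 0.28 it affects only estimated ratios of about 0.85-0.92 or 1.09-1.17 as n goes from 24 to 100. A ratio estimated at 1.00 passes at both sizes under Reading 1. The dose was chosen to match adult AUC (Protocol 5.6), and the documents state no expected ratio. Residual variability and weight spread are not modelled here.

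Two stronger readings are tempting and go too far. A reader might infer that the plan requires 1000 or more separate intervals to be judged. The text does not say so: the plural in Step 3 is explained by having two parameters, and a pooled ANOVA is equally possible. A reader might also take the 100 per age group in Protocol 5.6 as a competing size for Step 2. It describes completed dose-selection simulations, and 100 serves here only as one value above the floor.

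**Conclusion.** The point holds for the criterion as written in the protocol and SAP. The interval compared with 0.80-1.25 takes its width from a simulated n that has a floor but no fixed value, and it is undefined whether the ANOVA is per trial or pooled and how a verdict is reached. Under the stated assumptions the set of passing ratios runs from 0.92-1.09 (n = 24) to almost the whole of 0.80-1.25 (pooled). With a share-of-trials rule and identical true exposure, 72% of trials pass at n = 24 and about 100% at n = 100 without parameter uncertainty, or 38% and 66% with an assumed SE of 0.16.

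This does not show that the trial's verdict will be wrong or will reverse. Nor does failing Step 4 alter dosing within this study, since Step 5 only proposes regimens for later simulations. The point should be fixed because it concerns the only numeric test of a primary objective. Confidence is medium, because the PKAP was not available.

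**What to change.** In Steps 3-4, judge 0.80-1.25 against the 5th-95th percentile interval, across the bootstrap parameter sets already planned in Step 2, of the model-predicted adolescent:adult geometric mean AUC ratio over the dosing interval. Compute each ratio on one fixed, large simulated population with matched renal function, so that simulation noise is negligible and the width reflects parameter uncertainty. Do this for both age ranges named in Step 6. State in advance that an interval missing the limits only because it is wide is reported as inconclusive, not as non-equivalent.

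Keep the ANOVA simulations as supportive. Fix n per group and the per-trial or pooled rule before the model is fitted. Do not set n to the number enrolled: with a true ratio of 1.00 and no parameter uncertainty, only 60% of trials pass at n = 20 and 12% at n = 10. If the PKAP already settles these matters, cite it in Steps 2-4.

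The cost is wording and modest extra simulation, with no new data. The downside is a possibly less favourable result. At ratio 1.00 the interval fits only if the SE of the log ratio is below ln(1.25)/1.645 = 0.136, and the documents give no SE for this ratio. As illustrations, SE 0.113 gives exp(±1.645 × 0.113) = 0.83-1.20, which fits. SE 0.16 gives 0.77-1.30, which does not. The second case is more plausible for 12 to < 16 years, with 7 to 10 subjects, so the inconclusive category matters most there. Pooling with adult data may give smaller SEs.

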6.1. **Primary Objectives**

The primary objectives of this study are as follows:

Stage 1

- to characterize the PK of migalastat in adolescents with Fabry disease, and to validate extrapolation of migalastat plasma exposure in adults to adolescents weighing ≥ 45 kg for the 150 mg migalastat capsule administered QOD
- to evaluate the safety of migalastat treatment in pediatric subjects diagnosed with Fabry disease and who have *GLA* variants amenable to treatment with migalastat

Stage 2

• to evaluate the safety of migalastat treatment in pediatric subjects diagnosed with Fabry disease and who have *GLA* variants amenable to treatment with migalastat

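### Step 6 of the PK analysis concludes by the 80-125% rule for 12 to < 16 year olds, but Steps 3-4 specify a ratio and 90% CI only for the pooled 12 to < 18 group

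*Protocol*

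**What the plan says.** Protocol 11.3.2.3 sets out the comparison with adults in six steps.

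- **Step 2** simulates at least 1000 trials with at least 24 subjects per age group. It does not say which age groups.
- **Step 3** first has the endpoints "calculated from simulated concentration-time data in pediatric groups and in adults", in the plural and again unnamed. It then states that AUC and Cmax "in 12 to < 18 year olds will be compared to the values in adults with equivalent renal function", and that the 90% CIs "will be constructed for comparison of the pediatric group with adult group", now in the singular.
- **Step 4** declares equivalence when the 90% CI of the AUC ratio lies within 0.80-1.25, and judges only the intervals that Step 3 produced.
- **Step 6** opens "The proposed dose for pediatric subjects (12 to < 18 years and 12 to < 16 years" and settles the regimen for both groups by the 80-125% rule on AUC, with Cmax to meet the rule if possible.

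The 12 to < 16 group appears separately in two other places. Section 8.1 reserves at least 7 to 10 of about 20 subjects for a subgroup analysis at the end of Stage 1. Sections 11.3.2.1 and 11.3.2.3 describe that analysis as a graphical comparison of observed with predicted concentrations.

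The SAP (Sections 5.3 and 9) leaves all PK analysis to a separate PKAP.

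**The concern.** The conclusion in Step 6 needs an interval that no step specifies. As written, the 12 to < 16 statement can rest only on the pooled interval or on a plot without a pass rule.

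The under-16s are the reason the question matters. Section 5.6 says "Migalastat has not been studied in pediatric subjects under 16 years of age", whereas some 16 to < 18 year olds were in the Phase 3 studies. Pooling mixes the new ages with ages that already have data, so a difference confined to the younger group is diluted. The first Stage 1 primary objective (Section 6.1) is "to validate extrapolation of migalastat plasma exposure in adults to adolescents weighing" at least 45 kg. A reader will take an equivalence statement for 12 to < 16 as part of the answer to that objective, and the specified analysis would not support it for that group.

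**Working it through.** **Inputs from the documents**

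- 90% CI within 0.80-1.25 (Step 4); at least 24 simulated subjects per age group (Step 2).
- Inter-individual variability of clearance 28.5% (Section 11.2).
- At least 7 to 10 of about 20 subjects aged 12 to < 16 (Section 8.1). The share is therefore p = 7/20 = 35% or 10/20 = 50%.

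**Assumptions (not in the documents)**

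- 24 simulated adults.
- The simulated group has the same age mix as enrolment.
- Older adolescents have a ratio of 1.00 to adults.
- The interval is read per simulated trial, since the protocol does not say how at least 1000 intervals become one decision.

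**Check of the plan's own figure.** The equivalence steps state no power. Section 11.2 gives 7 subjects for at least 80% power at 28.5%. Taking the limits (0.6, 1.4), which Section 11.2 states only for its second method, power is about 88% with 7 subjects and 75% with 6, so 7 reproduces. The second method does not reproduce: with 10 subjects and 9 df its upper limit is 1.436, above 1.4. That is a separate matter, and nothing below depends on it.

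**Step A: width of the interval.** The log-scale SD is √ln(1 + 0.285²) = 0.2795. The half-width is t(0.95; 46) × 0.2795 × √(2/24) = 1.679 × 0.2795 × 0.2887 = 0.1354, a factor of e^0.1354 = 1.145. To pass, the observed ratio must lie between 0.80 × 1.145 = 0.916 and 1.25 / 1.145 = 1.092.

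**Step B: dilution.** The pooled ratio is (younger ratio)^p × (older ratio)^(1−p). With the older ratio at 1.00, a younger ratio of 1.25 and p = 0.35, the pooled ratio is 1.25^0.35 = 1.081.

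**Step C: does the pooled interval pass?** Mixing two groups adds variance p(1−p)(ln 1.25)² = 0.35 × 0.65 × 0.2231² = 0.0113 on the pediatric side. The SD becomes √[(0.0781 + 0.0113 + 0.0781)/2] = 0.289 and the half-width 1.679 × 0.289 × 0.2887 = 0.140. The expected CI is 1.081 ×/÷ 1.151 = 0.940-1.244, inside the limits. Simulating this test, the pooled comparison passes in about 50% of trials. The younger group compared alone, 24 versus 24, passes in about 5%.

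**Step D: largest younger ratio with a passing pooled expected CI** (older ratio 1.00, including the mixing variance)

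| Simulated per group | 35% share | 50% share |
|---|---|---|
| 24 | 1.27 | 1.18 |
| 100 | 1.53 | 1.36 |
| 1000 | 1.76 | 1.49 |

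Without the mixing variance, the 24-per-group figures are 1.0917^(1/0.35) = 1.28 and 1.0917^(1/0.50) = 1.19. Step 2 sets a minimum of 24 and no maximum, so the lower rows are also permitted.

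At 24 per group and a 50% share, the tolerated younger ratio of 1.18 is itself below 1.25. Its own 24-versus-24 interval would still reach 1.18 × 1.145 = 1.35 and fail Step 4.

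**The case against.** The strongest reply is that this is a drafting gap. Step 2 speaks of age groups and Step 3 of pediatric groups. Section 11.2 sizes each age/weight group for a statistical comparison with adults, and Step 6 names both groups. A separate 12 to < 16 interval may well be intended, and the PKAP may specify it. That stands as far as intent goes. It does not repair the protocol, where the sentences defining the comparison and its CI name 12 to < 18 only.

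Three stronger readings are tempting, and the documents do not support them.

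- **That the under-16s go untested.** They are in the pooled comparison and have their own visual check at the end of Stage 1. What is missing from the protocol is a separate ratio, interval and pass rule.
- **That the gap concerns the lightest subjects.** The 45 kg minimum applies at every age, and no weight distribution by age is given. Section 5.6 does say "Body weight also explains variability in the pharmacokinetics of migalastat in individuals < 70 kg", but Step 1 re-evaluates the allometric functions, and Section 7.2.1 cites simulations of exposure at 43 kg. No weight exponent is given, so the size of any effect near 45 kg cannot be worked out from the documents.
- **That the pooled ratio itself may rise to 1.25.** Step 4 judges the CI. With 24 per group the pooled point ratio must stay below about 1.09, so the masking is smaller than that reading suggests.

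**Conclusion.** The point holds as a mismatch between the groups for which Step 6 concludes and the one group for which Steps 3-4 specify a test. A pooled pass does not establish the 80-125% rule for 12 to < 16 year olds. At the minimum simulation size the pooled expected CI tolerates a younger ratio of about 1.27 (35% share) or 1.18-1.19 (50% share). A younger ratio at or above 1.25 therefore passes in expectation only with a low under-16 share, larger simulated groups or an older ratio below 1.00.

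These sizes rest on the assumed ratio of 1.00 in older subjects, 24 adults and an unchanged age mix. They show what the rule permits; they do not predict exposure in this trial. The mismatch itself needs no assumption. It should be corrected because it bears on a Stage 1 primary objective, subject to what the PKAP says.

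**What to change.** 1. In Step 2, name the age groups to be simulated.
2. In Steps 3-4, also compute the AUC and Cmax ratios with 90% CIs for 12 to < 16 against adults with equivalent renal function.
3. In Step 6, base the 12 to < 16 statement on that interval, or limit Step 6 to the group tested.
4. Align the protocol with the PKAP, or confirm that the PKAP already contains the comparison.

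A model-predicted AUC ratio near 45 kg, with its uncertainty, would be an optional extra output.

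The cost is some wording and one more comparison from simulations already planned, with no new subjects or samples. The added comparison may fail where the pooled one passes. With 24 versus 24 and CV 28.5%, the chance of passing per simulated trial is about 72% at a true ratio of 1.00 and 45% at 1.10. The interval will be wider if fewer subjects are simulated in that group.
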